5.2 Study Assessments

Table 1: Schedule of Events: **1** = In-Person; **2** = Telephone; **3** = Subject Self-Tracking

Time Point (Days)	Screen / enroll	D19	D4	D7	D10	D14	D21	D28	D42	D60	ET ¹⁰
STUDY TEAM											
Inclusion / Exclusion	İ										
Consent	İ							\			
Screening Tests ^{1, 12}	İ					1					
Demographics	İ										
CXR or CT ¹³	İ										
Physical Exam	İ			İ		1	Ť	Ţ			ţ
Vitals ²	İ			İ		İ	İ	İ			İ
EKG	İ			İ		İ	İ	İ			İ
CoV-2 N/P ³	İ					İ		Ť			Ť
Standard labs ^{4, 12}	İ			İ		Ì		Ť			Ť
Blood draws ^{5, 12}	İ			İ		1	Ť	Ť			İ
Immunology tests ^{6, 12}	İ			İ		Ì	Ť	Ť			Ť
CoV-2 blood ^{7, 12}								Ť			Ť
AE assessment	İ	2	2	İ	2	Ţ	İ	Ī	2	~	Ĭ
Symptoms assessment	İ	2	2	İ	2	Ţ	İ	İ	2	~	İ
WHO 9-Point Scale ⁸	İ	2	2	İ	2	Ţ	İ	İ	2	2	İ

SUBJECTS (as recorded in study diary)						
IP/placebo intake	Three times per day through day 28 or ET					
Temperature ¹¹	Daily via thermometer through day 28 or ET; subject will report via telephone to					
	study team at Day 42 & 60					
SpO2 resting ¹¹	Daily via pulse oximeter through day 28 or ET; subject will report via telephone to					
	study team at Day 42 & 60					
Symptom tracking	legistrian One time per day through day 28 or ET; subject will report via telephone to study					
	team at Day 42 & 60					

¹Screening tests: HIV, Hepatitis B, Hepatitis C, and pregnancy (serum pregnancy test for women of child-bearing potential per MedStar definition at enrollment and at day 14).

²Vital signs: oral temperature, heart rate, systolic blood pressure.

³Quantitative nasopharyngeal SARS-CoV-2 RNA testing (RT-PCR): nasopharyngeal or throat swabs will be used; any FDA-approved or commercial testing method will be acceptable. A home health agency may be used to confirm COVID-19 by RT-PCR in the subjects' home in the event their initial testing did not include PCR, to ensure expeditious resulting and appropriate inclusion into the trial. If home health is used to collect the PCR test or there is a delay in PCR resulting at initial screening, the subject will return to either MedStar Washington Hospital Center or MedStar Franklin Square for completion of the screening/enrollment visit in 1 to 3 days, once positive PCR is confirmed, to complete all study procedures including randomization and medication dosing under observation. ⁴Standard labs: serum chemistry, coagulation tests and hematology. Pregnancy tests for women of childbearing potential at screening, day 14 and end of treatment.

⁵Blood draws: serum and peripheral blood mononuclear cells for later immunological analysis.

- ⁹Day 1 (i.e., the first day of drug intake) is most likely also the screen / enroll day; subjects will receive a phone call from Study Team a few hours after first dose is taken to check up on how they are doing.
- ¹⁰ET: Subjects who prematurely discontinue study drug for any reason are asked to have an Early Termination (ET) visit the day the last study drug dose was taken.
- ¹¹ Subjects will be given a digital thermometer and portable pulse oximeter to record their temperature and oxygenation daily in the provided subject diary.
- ¹² These laboratory tests will be collected at a one-time blood draw at each visit, a total of 5 collections at the 5 visits (Screening, Day 7, Day 14, Day 21, and Day 28). The amount drawn at each timepoint is as follows: Screening visit (56 mL or 11 teaspoons), Day 7 (44 mL or 9 teaspoons), Day 14 (56 mL or 11 teaspoons), Day 21 (20 mL or 4 teaspoons), and Day 28 (48 mL or 10 teaspoons). The early termination visit would be in lieu of one of the in-person visits, it is not included in the total. Laboratory tests collected at the screening/enrollment visit may be collected by a home health agency in the subjects' home.

¹³Chest x-ray or CT of the chest will be completed as standard of care but not required for screening or randomization or enrollment

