3.4 Secondary Endpoints

1. Clinical recovery and resolution of COVID-19 symptoms

1a. Sustained recovery and resolution rates of common COVID-19 symptoms:

(i.e., stuffy or runny nose, sore throat, cough, low energy or tiredness, muscle or body ache, headache, chills or shivering, feeling hot or feverish, nausea, vomiting, diarrhea, shortness of breath with exertion; impairment in sense of smell or taste)

Proportion of subjects in treatment group versus placebo group, respectively, who per symptom questionnaire on days 4, 7, 10, 14, 21, 28, 42, 60 post randomization have achieved for two consecutive days:

- o scores not higher than 0 for all symptoms
- o scores not higher than 1 for all symptoms
- o scores not higher than 0 for all symptoms other than impairment of taste or smell
- o scores not higher than 1 for all symptoms other than impairment of taste or smell
- *1b. Sustained improvement of global impression rates:* Proportion of subjects in treatment group versus placebo group, respectively, who per symptom questionnaire on days 4, 7, 10, 14, 21, 28, 42, 60 post randomization have answered for two consecutive days
 - "Yes" to "In the past 24 hours, have you returned to your usual health (before your COVID-19 illness)?"
 - "Yes" to "In the past 24 hours, have you returned to your usual activities (before your COVID-19 illness)?"
 - o "None" to "In the past 24 hours, what was the severity of your overall COVID-19 related symptoms at their worst?"
 - o "Mild" to "In the past 24 hours, what was the severity of your overall COVID-19 related symptoms at their worst?"
- 1c. Time to sustained recovery, resolution or improvement: comparison in treatment group versus placebo group, respectively of the number of days from randomization to the first day of achieving each item in 1a and 1b above.

2. Physical functions and parameters relevant to COVID-19

- **2a. Parameter rates:** Proportion of subjects in treatment group versus placebo group, respectively, who on days 4, 7, 10, 14, 21, 28, 42, 60 post randomization per thermometer or pulse oximeter reading experienced:
 - fever at any point between enrollment and day 2 post randomization and who were afebrile <38C
 - o oxygenation of SpO2>=96% or >93% in room air when resting
- 2b. Time to and length of parameters: comparison in treatment group versus placebo group, respectively of the number of days

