 - o from randomization to the first day of achieving sustained (i.e., at least 2 days) resolution of fever for subjects who presented with fever at any point between enrollment and day 2 post randomization

- with temperature <38C or >=38C experienced in total during the first 28 days post randomization
- o from randomization to the first day post randomization of achieving oxygenation of SpO2>=96% in room air when resting for subjects who presented with SpO2>93% and <96% in room air, when resting, at enrollment
- o with oxygenation of SpO2>= 96% or SpO2>93% in room air, when resting, in total during the first 28 days post randomization

3. COVID-19 related deterioration and mortality

- **3a. Deterioration and mortality rates:** Proportion of treatment group, versus placebo group, respectively, who per subject reporting or medical records by day 14, day 28 and by day 60 post randomization had experienced:
 - o an emergency department visit, other than at study enrollment or study visits
 - hospitalization for COVID-19
 - o hospitalization for COVID-19 requiring oxygen
 - hospitalization for COVID-19 requiring ICU
 - o hospitalization for COVID-19 requiring ventilation
 - o COVID-19 related death
 - death
 - hospitalization or death
- **3b.** *Time to and length of deterioration*: Comparison of treatment group versus placebo group, respectively, in the number of days
 - o from randomization until the first day of experiencing hospitalization for COVID-19
 - o of hospitalization for COVID-19 experienced in total by day 14, by day 28 and by day 60 post randomization
 - o of hospitalization for COVID-19 requiring oxygen experienced in total by day 14, by day 28 and by day 60 post randomization
 - of hospitalization for COVID-19 requiring ICU experienced in total by day 14, by day 28 and by day 60 post randomization
 - o of hospitalization for COVID-19 requiring ventilation experienced in total by day 14, by day 28 and by day 60 post randomization

4. WHO 9-Point Ordinal Scale

- 0. Uninfected or "no clinical or virological evidence of infection"
 - a. defined as subject answering "Yes" to "In the past 24 hours, have you returned to your usual health (before your COVID-19 illness)?"
- 1. Not hospitalized, no limitations on activities
 - a. defined as subject answering "Yes" to "In the past 24 hours, have you returned to your usual activities (before your COVID-19 illness)?"
- 2. Not hospitalized, limitation on activities

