 - a. defined as subject answering "No" to "In the past 24 hours, have you returned to your usual activities (before your COVID-19 illness)?"
- 3. Hospitalized, not requiring supplemental oxygen
- 4. Hospitalized, requiring supplemental oxygen
- 5. Hospitalized, on non-invasive ventilation or high flow oxygen devices
- 6. Hospitalized, intubated
- 7. Hospitalized, advanced life support including invasive mechanical ventilation or ECMO
- 8. Death
- **4a)** Ordinal scale rates: proportion of treatment group versus placebo group, respectively who had experienced:
 - o an improvement from scale 2 at randomization to scale 1 or 0 on days 4, 7, 10, 14, 21, 28, 42, 60 post randomization,
 - o an improvement from scale 1 at randomization to scale 0 on days 4, 7, 10, 14, 21, 28, 42, 60 post randomization
 - o a sustainment from scale 1 at randomization to scale 1 on days 4, 7, 10, 14, 21, 28, 42, 60 post randomization
 - o any improvement of the scale (i.e., at least a 1-point decrease) between enrollment and days 7, 14, 28, 42, 60 post randomization
 - any worsening of the scale (i.e., at least a 1-point increase) between enrollment and days 7,
 14, 28, 42, 60 post randomization
 - o scale 4 or higher by day 28 or day 60 post randomization
 - o scale 6 or higher by day 28 or day 60 post randomization

- *4b) Ordinal scale averages, highs, and lows:* Comparison of treatment group versus placebo group, respectively, at days 14, 28 and 60 post randomization in the
 - o average of daily scale value on that day
 - o overall average of daily scale value experienced since enrollment
 - o in the worst (i.e., highest) daily scale value experienced since enrollment
 - o in the best (i.e., lowest) daily scale value experienced since enrollment
- **4c)** Time to improvement: Comparison of treatment group versus placebo group, respectively, in the number of days from enrollment until first experiencing a 1-point improvement sustained over at least 2 days by day 14, day 28 and by day 60 post randomization
- *4d) Length of ordinal scale experience:* Comparison of treatment group versus placebo group, respectively, in the total number of days by day 14, day 28 and by day 60 post randomization on which subjects experienced a given scale value (i.e., 3, 4, 5, 6, 7)

5. Surrogate markers of COVID-19-related inflammation and organ involvement

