The trial duration will be approximately 60 days (8.5 weeks) for all subjects enrolled. As outlined in the Schedule of Events Table in Section 5.2, over the course of the study duration, all subjects will use a diary to record IP intake as well as symptoms and activity levels with guidance to do so at the same time each day; assess physical parameters using a study-provided thermometer and pulse oximeter for which detailed instructions will be provided at enrollment; be assessed at regular intervals by the Study Team via telephone calls and in-person follow-up clinic visits; and give blood for laboratory tests.

An experienced and appropriately licensed Study Team member will conduct the telephone study visits and be the point of contact if subjects experience deterioration, such as high temperatures (above 38C) or low oxygen saturation levels (below 93%). The primary coordinator of the trial will be a registered nurse, experienced in vital sign and symptom review, with the ability to escalate any medical concerns to the Principal Investigator as it relates to worsening of the subjects' illness or adverse event identification. The Principal Investigator or delegated Sub-Investigator, as documented on the study delegation log, is well-versed in delegation of appropriate tasks as defined by licensure and scope of practice and will work closely with the study team to assure delegation remains appropriate through the duration of the trial. Medical advice or direction will only be given by sufficiently licensed study personnel, either mid-level providers or physicians, in partnership with their primary care team.

Subjects will be instructed to fill in symptoms assessment, overall health assessment, temperature and oxygen saturation levels in the diary each morning; and to note in the diary 3 times per day that they have taken the study drug. The Study Team will conduct in-person visits with the subjects on days 7, 14, 21, and 28 and telephonic visits with subjects on days 1, 4, 10, 42, and 60; as well as when / if subjects contact them due to symptom deterioration as instructed. Subjects will receive reminders to complete the diary via text message and / or email. Subjects who prematurely discontinue study drug for any reason will be asked to have an Early Termination (ET) visit the day the last study drug dose is administered; moreover, they will be encouraged to stay enrolled so that further safety and outcome information can be collected and analyzed.

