12.2 Illustrative Subject Diary Excerpts

Subject Diary – Overview of Study Events Days Week 1 Week 2 Week 3 Week 4 Week 5 Week 6 Week 7 Week 8 Week 9

Legend

Days 1-28: Three times per day: take the study drug; Once every morning: rate your symptoms and overall health and record your temperature and oxygen saturation levels

Days 1, 4, 10, 42, 60: Receive phone calls from Study Team

Days 7, 14, 21, 28: Visit Study Center in person

Days 7, 14, 21, 28: Give Study Team last 7 days of Diary pages

	me you are this out to	-		
None	Mild	Moderate	Severe	
			·	
e these IS :	SUES ? Place	an X		
0	1-2	3-4	5 or mo	
tilles	times	tilles	l tilles	
			-	
			I have NO sense	
as usua	i tha	nusual		
	0 times our SENSES SAME as usua	0 1-2 times our SENSES? Place an SAME as usual tha	times times times our SENSES? Place an X SAME LESS	

e:	Subject Nu	mbe	r:			
Global Health Impression Place an X	Time you are filling this out today:					
	None	IV	lild	Moder	ate	Severe
In the past 24 hours, what was the severity of your OVERALL COVID-19-related symptoms at their worst?						
			Yes			No
	•					
	-					
Temperature			Tempo	erature		Time
Record your temperature from the thermothe time you took the measurement; if you	r temperature from the thermometer and note u took the measurement; if your temperature			٥F		am
Oxygen (O₂) Saturation			O ₂ Sat	uration		Time
note the time you took the measurement;	if your oxygen			%SpO ₂		am
	Marris		D/I:	l Dov		Fuening
	WOTHIN	ıg 	IVIIC	i-Day		Evening
3 tablets of the STUDY DRUG and note the time you took them; remember you		am		_m		pn
, , , , , , , , , , , , , , , , , , , ,						
will take 9 tablets total each day	Nam	ne		Dose_		Time_
,	Nam	ne .		Dose		Time

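### Table 1 schedules no two consecutive days of symptom data after day 28, so several day-42 and day-60 endpoints cannot be obtained as defined; its ET cut-off also contradicts section 7.2

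*Combined protocol and SAP*

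**What the plan says.** **Endpoints (3.4, repeated in the synopsis).** 1a counts subjects who "on days 4, 7, 10, 14, 21, 28, 42, 60 post randomization have achieved for two consecutive days" reach given symptom scores. 1b applies the same days and the same two-day rule to the global health questions. 4b compares, at days 14, 28 and 60, the "overall average of daily scale value experienced since enrollment", the value on the day itself, and the best and worst values (for example "in the worst (i.e., highest) daily scale value experienced since enrollment"). 4c is time to a 1-point improvement held for at least two days, with horizons at days 14, 28 and 60. WHO levels 0 to 2 are defined by diary questions about the past 24 hours.

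**Collection.** Table 1 sets symptom tracking "One time per day through day 28 or ET; subject will report via telephone to study" team at days 42 and 60; temperature and SpO2 follow the same pattern. The diary legend (12.2) reads "Days 1-28: Three times per day: take the study drug; Once every morning: rate your symptoms and overall health". In-person visits end at day 28. Section 5.1 lists "telephonic visits with subjects on days 1, 4, 10, 42, and 60", plus contacts that subjects start when they deteriorate. Yet 5.1 also describes diary use across the whole study, and its paragraphs on background care promise diary-based collection for a minimum of 60 days.

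**Stopping study drug.** Footnote 10 of Table 1 places the ET visit on the day of the last dose when drug is stopped early. Section 7.2 tells subjects who stop drug to go on with the diary and visits. Sections 5.3 and 8.1 continue data collection to day 60 while consent lasts.

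**Markers.** 5a and 5b list day 21 for every marker.

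**The concern.** A two-day criterion needs two adjacent observed days, and an average of daily values needs daily values. If the diary ends at day 28, the day-42 and day-60 versions of these endpoints have no matching data. The analyst would have to choose between a one-day status, a carried-forward status and an average over unequal periods, and the plan does not say which.

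The ET wording raises a separate question. Section 5.3 expects some subjects to stop drug because of side effects or because their symptoms have gone. If the diary stops with the drug, the missing days depend on outcome.

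This matters because section 8.7 gives the trial's purpose as supplying an effect size for a larger trial. A result labelled day 60 that mostly or wholly reflects days 1 to 28 would mislead the planners of that trial.

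**Working it through.** The plan gives no figure of its own on this point, and the power statement in 8.7 plays no part. The check counts what the schedule supplies.

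**Observed days.** Inputs: diary on days 1 to 28 (Table 1, 12.2) and contacts on days 1, 4, 7, 10, 14, 21, 28, 42 and 60 (5.1).
- Days 1–60: 28 + 2 = 30 of 60 observed. Days 29–60: 2 of 32.
- Consecutive-day pairs ending by day 28: 27 of 27. Pairs ending on days 29–60: 0 of 32.
- Endpoint days 4, 7, 10, 14, 21 and 28 each have a pair. Days 42 and 60 have none.

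**1a and 1b.** (4 + 4) items × 8 days = 64 proportions, of which 8 × 2 days = 16 fall on days 42 and 60. Read as current status, these cannot be evaluated. Read as achieved by that day, they repeat day 28.

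**4c and 1c.** Subjects enroll non-hospitalized, so their scale is 2 or lower, and improvement from enrollment means level 1 or 0. Those levels come from the diary questions, not hospital records. No two-day outpatient event after day 28 can be seen, so 4c by day 60 equals 4c by day 28. With no event times after day 28, the Cox risk sets, and hence the hazard ratio, are the same whether event-free subjects are censored at day 28 or day 60. Section 8.6 uses data up to dropout, which gives no censoring day for an event-free subject who completes day 60.

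**4b average at day 60.** Let m1 and m2 be the mean scale over days 1–28 and 29–60. Assume a non-hospitalized subject, a simple mean of the collected values, and two calls that average m2.
- Collected: (28·m1 + 2·m2)/30. Full: (28·m1 + 32·m2)/60.
- Difference: 28(m1 − m2)/60 = 0.467(m1 − m2).
- Scale 2 to day 28, then 0: collected 56/30 = 1.87, full 56/60 = 0.93. Constant scale: no error.
- Between-arm difference confined to days 1–28: recorded at (28/30)/(28/60) = 2 times its 60-day value. Equal throughout: 1 time. Confined to days 29–60: (2/30)/(32/60) = one-eighth.
- Everyone at 0 from day 29: every value doubles, so the standardized effect is unchanged.

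**4b worst and best at day 60.** Levels 3 to 8 can come from medical records. Levels 0 to 2 cannot: a subject enrolled at level 1 who reaches 2 only between the late calls is missed.

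**Share of outputs.** Counting item-by-day outputs in areas 1–4 of 3.4: 64 + 8 (1c) + 24 (2a) + 6 (2b) + 24 (3a) + 13 (3b) + 38 (4a) + 12 (4b) + 3 (4c) + 15 (4d) = 207. Affected: 16 + 1 (4b average) + 1 (4c) = 18, or 8.7%. The worst and best values, affected in part, are two more.

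**ET, only if Table 1 is followed.** Stopping on day 7, 14 or 21 loses 21, 14 or 7 of 28 diary days (75%, 50%, 25%). With ET on day 10, 9 of 27 pairs remain, and days 14, 21 and 28 have single visit values without a pair. One misclassified subject is 1/20 = 5 percentage points of an arm.

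**Markers.** Section 3.4 names 42: 31 standard labs, 9 immunology, 2 virology. As Table 1 is extracted, standard labs, viral load and serology have no day-21 mark, so 31 + 2 = 33 of 42 have no day-21 test. If the white cell count and four differential counts are run with immunology, 33 − 5 = 28. The smaller day-21 blood volume (20 mL, against 44 mL at day 7) agrees with this, as do the liver-test days listed in 7.7, although 7.7 also speaks of weekly testing.

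**The case against.** The strongest reply is that 5.1 keeps diary collection going for 60 days, so nothing is missing. That stands as evidence of a conflict, not as a rescue: Table 1 and the subject's own diary legend say day 28, and the version 2.1 change summary suggests that day 28 was deliberate.

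A caller could ask about two days, but no section says so. The 24-hour window is legible for the global questions; no recall window for the 1a symptom items can be read in the diary excerpt.

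Other replies carry weight. The trial generates hypotheses, section 1.3 expects uncomplicated illness to last 12–15 days, and most recoveries may fall before day 28. No section prescribes the simple mean assumed for 4b. Section 5.3 also uses early termination for withdrawal from the study, where ending the diary makes sense, and scheduled visits would still supply single symptom assessments after ET.

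A reader might infer that day-60 results fail generally. The documents do not support that. Endpoint 3a is taken "per subject reporting or medical records by day 14, day 28 and by day 60 post randomization had experienced" the event. Endpoint 4d, the "total number of days by day 14, day 28 and by day 60 post randomization on which subjects experienced" a given level, covers levels 3 to 7, all in hospital. The adverse-event endpoint does not use the diary. A reader might also infer a known bias between arms from early stopping; no section gives the number of subjects who will stop, when, or in which arm.

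**Conclusion.** The point holds and should be corrected, at moderate weight. Under Table 1, the 1a/1b outputs at days 42 and 60 are either not evaluable or repeat day 28, 4c by day 60 repeats day 28, and the 4b day-60 average covers mainly days 1–28. The 4b worst and best values share the gap for levels 0 to 2. The 4b error may be zero or substantial and can take either sign; its size depends on the averaging rule and on the course after day 28. Events up to day 28 remain estimable. The primary endpoint, 3a, 3b, 4d and single-day values are intact.

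The ET cut-off is a genuine contradiction with 7.2, 5.3 and 8.1. Its harm is conditional on sites following Table 1. Any loss would then be related to outcome, but its size is unknown.

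The day-21 marker mismatch is minor, applies to both arms alike, and rests on a table whose layout may be damaged.

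**What to change.** 1. Reconcile 5.1 with Table 1 and 12.2 on the length of the diary.
2. If day 28 stands, amend 3.4 and the synopsis:
   - Define 1a and 1b at days 42 and 60 as the status reported at that call, or collect the diary questions on days 41–42 and 59–60.
   - Limit the 4b since-enrollment average to day 28.
   - Label the day-60 worst and best values as based on the diary to day 28, the two calls and medical records.
   - Drop the 4c day-60 horizon unless the two-day prompts are added.
3. In 8.5 and 8.6, censor event-free non-hospitalized subjects in 1c and 4c at their last evaluable diary day.
4. In Table 1, end only the study-drug intake row at ET. Run the temperature, SpO2 and symptom rows through day 28, including after study drug is stopped, unless consent is withdrawn.
5. Check the day-21 marks against the original table and give marker-specific days in 5a and 5b.

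Cost: wording, plus an amendment through the IRB and FDA (7.17, 10.11). No new visit or blood draw is needed. The optional prompts add days 41 and 59, or 2 × 40 = 80 diary entries. Section 7.2 already requires the diary after study drug is stopped. The rules should be fixed before unblinding.
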